1 BACKGROUND

The key challenge of HIV eradication strategies is persistence of a small pool of resting memory CD4+ T cells that harbor latent replication-competent HIV, untouched by current antiretroviral therapy (ART).³ One potential strategy to eliminate this reservoir is a “shock and kill” approach in which agents designed to reverse latency (latency reactivating agents, LRAs) are used to “shock” the virus out of these cells in order for the host immune response, ART, and/or additional immunomodulatory agents can then eliminate virus-expressing cells.⁴⁻⁷ The goal of the current proposal is to evaluate the *in vivo* biological response to an herbal supplement used in traditional Chinese medicine (“kansui”) that has potent *in vitro* latency reactivating capabilities.

Kansui has been prescribed in Chinese medicine for thousands of years as a cathartic agent. It is typically given as a single dose of 0.5 -1.5 grams, and is used to treat intestinal obstruction, nodular skin lesions, water retention, and epilepsy.^{8,9} Kansui extract is made from the *Euphorbia* root and is thought to contain several potentially biologically active components, including a large number of ingenols, which are known to activate and/or interrupt a number of cellular pathways, including some known to be involved in the maintenance of HIV latency.¹⁰⁻¹² Recently, a semi-synthetic version of ingenol from *Euphorbia tirucalli* has been developed as Ing B (Ing B).¹³ Ing B demonstrates the potent ability to reactivate latent HIV in *ex vivo* and non-human primate models.^{11,12,14} Ing B was shown to induce significant immune activation (upregulation of CD38, HLA-DR, CD69 expression on CD4+ T cells) and reactivate virus in both untreated and ART-suppressed SIVmac251-infected rhesus macaques without hypercytokinemia.^{14,15} These effects were observed as early as three days in untreated monkeys¹⁵ to approximately 30 days post-Ing B in ART-suppressed monkeys.¹⁴ The ability to induce T cell activation and viral reactivation were even more pronounced when Ing B was administered concomitantly with another LRA called suberanilohydroxamic acid (SAHA).¹⁴

Kansui contains ingenols that induce immune activation and reactivate latent HIV-1

[figure not shown]
Several compounds have already been tested to reactivate latent HIV, including histone deacetylase inhibitors such as suberoylanilide hydroxamic acid (SAHA)¹⁶ and protein kinase C (PKC) agonists such as prostratin¹⁷ and bryostatin.¹⁸ More recently, a new semi-synthetic ingenol ester that acts as a PKC agonist, 3-caproyl-ingenol (Ingenol B, or Ing B, patent-pending), has been tested in both J-Lat cell lines and in primary resting CD4+ T cells.¹¹⁻¹³ Ing B induced high levels of viral reactivation beyond those induced by SAHA, TNF-a, phorbol 12-myristate 13-acetate (PMA), or hexamethylene bisacetamide (HMBA) with minimal cellular toxicity.¹² In addition, Ing B was found to act synergistically with a BET bromodomain inhibitor (JQ1) or HMBA *in vitro*. Ing B promotes PKC activation and NF-kB nuclear translocation, and also upregulation of P-TEFb (which plays a critical role in HIV-1 transcriptional elongation). Therefore, ingenols may have multiple functions in promoting latent HIV reactivation.¹² Administration of Ing B has also been shown to increase the circulating viral load in untreated SIVmac251-infected monkeys as well as to reactivate virus from resting CD4+ T cells in ART-treated SIVDeltaB670+SIV17E-Fr-infected monkeys.¹⁵ Among untreated rhesus macaques, Ing B induces immune activation, upregulating CD38, HLA-DR, and

CD69 expression on CD4+ T cells.¹⁵ In all instances, no significant toxicity was observed.

1.1 Overview of Pre-Clinical Studies

1.1.a. Kansui is a potent activator of *in vitro* HIV-1 transcription

Based on *in vitro* bioassays performed in [name]'s lab, *Euphorbia kansui* extract powder is a potent activator of HIV transcription in latently infected Jurkat cells.¹⁹ From these experiments, 1 μ M of Ing B was estimated to possess equivalent bioactivity as 10 μ L/mL of *Euphorbia kansui* extract, suggesting a ratio of up to but not greater than 1:100 of Ing B to kansui. Since there are up to 12 different ingenols that could differ in their potency in the *Euphorbia kansui* powder, this range could be smaller. Importantly, *Euphorbia kansui* reactivated virus in patient peripheral blood mononuclear cell (PMBC) samples from HIV-infected ART-suppressed individuals (Figure 1), and a combination of *Euphorbia kansui* and vorinostat (a histone deacetylase inhibitor and also a latent reactivating agent) or JQ1 (a bromodomain inhibitor and latent reactivating agent) resulted in synergistic reactivation of latent HIV at suboptimal concentrations. Taken together, these results demonstrated that *Euphorbia kansui* functioned as a potent PKC agonist to reactivate latent HIV, which may be later used in combination with another HIV latent reactivating agent (LRA). In addition, [name] lab tested the stability and potency of the kansui powder over time (stored at room temperature) and has not observed any loss of biological activity (latency reversal). These results have been internally validated in the lab of our clinical trial study collaborator, [name], at the University of Utah. In a separate study published by another group, the researchers

identified an ingenol derivative (EK-16A) from *Euphorbia kansui*. They determined that this derivative of *kansui*, EK-16A, was 200-fold more potent than prostratin (a strong protein kinase C agonist) in reactivating HIV-1 from latently infected cell lines and primary HIV+ patient cells.²⁰ They also found that EK-16A exhibited synergy with other LRAs in reactivating latent HIV-1.

1.1.b. Non-human primate study

In collaboration with [name] (University of California, Davis), we have completed a non-human primate study to evaluate the safety of *Euphorbia kansui* prepared as tea, given at increasing dose and frequency to three juvenile SIVmac251-infected rhesus macaques compared to two controls (Figure 2). The rhesus macaques studied were part of an NIH-funded study (R01-AI118451, PI:[name]). Three juvenile male rhesus macaques (RM) were infected with SIVmac251 by intravenous administration. Two juvenile male RMs were included as “control” animals to receive early ART but no other *kansui* therapy. After 7 days post-infection, the three RM in the treated group began a treatment regimen of once daily subcutaneous injections of tenofovir (TFV, Gilead) 20 mg/kg subcutaneously daily; emtricitabine (FTC, Gilead) 50 mg/kg subcutaneously daily; dolutegravir (DTG, ViiV) 3.25 mg/kg subcutaneously daily for a period of 12 weeks. The three animals assigned to receive *kansui* were administered *kansui* at an initial safety dose of 5 mg/kg *Euphorbia kansui* powder prepared as tea was given via oral gavage, a dose equivalent to 1/4 the dose administered in traditional Chinese medicine (~0.25 g, or 5 mg/kg/day = 20 mg x 1 in a typical 4 kg juvenile RM). The animals were then followed for a 2-week washout period. Once safety goals were achieved with this initial dosing, the same treated animals then received *kansui* at 20 mg/kg/day = 80 mg x 1 and followed for another 2 week period. Next, after safety goals were achieved at this second dosing, the same three RM received *kansui* at 200 mg/kg/day = 800 mg x 2 consecutive days and followed for 2 weeks. Finally, after safety goals were achieved at this third dosing, the same three RM received *kansui* at 200 mg/kg/day = 800 mg x 3 consecutive days and followed for 3 weeks. At the end of this fourth dose 2-week washout period, the animals were followed for an additional 2-week follow-up period before undergoing necropsy.

Given that the animals demonstrated tolerability to an initial safety dose of 5 mg/kg *kansui*, treatment doses of 20 mg/kg *kansui* were administered at increased frequency in 2-week washout period intervals. Even at the highest frequency, 20 mg/kg *kansui* given

[figure not shown]

Figure 2. Study design of the non-human primate study. Kansui-treated rhesus macaques received doses as shown above with 2-week washout periods. Control monkeys did not receive placebo but were started on antiretroviral therapy (ART) and followed over the time as the kansui-treated animals.

for 3 consecutive days, no adverse clinical events (i.e., the expected and anecdotally reported events such as diarrhea). This initial work demonstrates that *Euphorbia kansui* extract powder, administered at weight-based dosing equivalent to that given in traditional Chinese medicine (20 mg/kg) for up to 3 days was well tolerated in rhesus macaques.

[figure not shown]

Figure 3. Kansui-treated animals demonstrated increased natural killer (NK) cell expansion (A) and increased activation markers on CD11b++CD11c- monocytes by percent expression and mean fluorescence intensity (B). Two of the three kansui-treated monkeys

In addition, we observed evidence for low levels of biologic efficacy in this small study such as increased natural killer cell expansion (measured as CD3-CD8+ cells) and increased activation markers on CD11b++CD11c- monocytes (Figure 3). Most strikingly, we observed a decrease in the size of the viral reservoir (SIV DNA) with evidence of increased SIV transcription (RNA) in two of the three kansui-treated monkeys (measured as cell-associated SIV DNA and RNA, respectively, from PBMCs). We are currently proceeding with performing the virologic assays on the necropsy tissues and performing additional immunophenotyping assays.

1.2 Overview of Clinical Studies

Kansui is well tolerated at doses prescribed in traditional Chinese medicine

Kansui is made by grinding up the root of *Euphorbia* plants into powdered form and is known to have a bitter taste.²¹ Per traditional Chinese medicine practices, kansui is efficacious and well tolerated at doses ranging from 1 gram to 8 grams for adults, given as a single dose, above which mild diarrhea has been reported.^{8,9} Mice studies suggest that at extremely high doses of 1.2 grams/kg given orally as a single dose (approximately

84 grams for a 70 kg human) *Euphorbia kansui* extract can induce severe diarrhea with abdominal distension and evidence of acute inflammatory intestinal injury.²² But these abnormalities were not observed at the lower doses studied (0.3 and 0.6 grams/kg, equivalent to 21 and 42 grams, respectively, for a 70 kg human), only slight changes in intestinal relaxation, secretion, and motility. Other potential side effects shown in mice include mild perturbations in glycolysis and amino acid and lipid metabolism.²³

Ingenols are one of many diterpenoid forms isolated from the sap of plants of the genus *Euphorbia*.¹³ The root of *Euphorbia*, processed into powdered or liquid form, has long been used in traditional Chinese medicine to treat medical conditions such as edema, pleural effusion, urinary retention, and cancer.^{8,9,24-26} *Euphorbia kansui* is one of the most commonly used *Euphorbia* in traditional Chinese medicine, which is prescribed as an herbal supplement known as “kan sui.”^{27,28} Various chemical constituents have been identified in *Euphorbia* plants, including sesquiterpenoids, diterpenoids (which includes ingenanes), triterpenoids, and phenol derivatives.²¹ The constituents thought to play a role in latent HIV reactivation include ingenols,¹⁰⁻¹² but euphols^{29,30} and other chemical constituents³¹ may also be biologically active. Recently, ingenol mebutate, has been FDA-approved for the topical treatment of actinic keratosis.²⁴

2 STUDY RATIONALE

Millions HIV-infected individuals are now receiving life-saving antiretroviral therapy.³² However, mortality remains high, particularly in resource-limited countries.³³ Moreover, chronic HIV-infected individuals demonstrate persistent immune activation despite ART-mediated viral suppression, which is an independent predictor of mortality in this setting.³⁴ Given the current absence of an effective HIV vaccine, finding a cure for HIV will likely have a large impact on the long-term health of ART-treated HIV-infected individuals, in particular for those living in resource-limited settings.

Kansui is an inexpensive, readily available herbal supplement prescribed for thousands of years in traditional Chinese medicine^{8,9} and contains active compounds such as ingenols that have been shown to reverse latency in an animal model. A semi-synthetic form of ingenol has been shown to potently reactivate latent SIV in rhesus macaques and is currently undergoing early drug development.¹¹⁻¹³ A human clinical trial testing a non-pharmacologic agent to treat HIV disease will be challenging unless we can demonstrate evidence of both safety and *in vivo* biologic activity. Though kansui has been studied extensively in traditional Chinese medicine, the herbal supplement has never been evaluated for biologic activity using Western scientific research methods.

Per discussions with the Department of Herbal Medicine at the American College of Traditional Chinese Medicine in San Francisco, kansui administration leads to clinical elimination of feces within two hours after administration of a single 1 gram dose of *Euphorbia kansui* extract powder, measured by weight, boiled with water, and prepared as a tea, suggesting rapid absorption and bioavailability. In mice, *Euphorbia kansui* extract potentiates time of fecal excretion but not overall quantity of fecal mass.²² This pilot study will provide key preliminary data to test the safety of low doses of *Euphorbia kansui* extract powder (1 gram daily for a single or 3 consecutive doses) prepared as tea

and confirm *in vivo* human biologic activity of kansui. This study will provide important preliminary data for future studies to perform a larger, more comprehensive clinical and pharmacokinetic/pharmacodynamics (PK/PD) study of kansui.

2.1 Risk / Benefit Assessment

The most significant potential benefit of this study is to contribute to the study of an inexpensive, non-pharmacologic agent for the possible use in future HIV cure strategies. The study will generate key preliminary data for investigating an agent that may have similar potency to a semi-synthetic compound currently undergoing early drug development. The collaborations formed as part of this study will provide a foundation for future larger studies evaluating similar botanicals for the use in HIV cure trials. The benefits of this short-term treatment with *Euphorbia kansui* extract powder prepared as tea (up to 3 days of dosing) outweigh the potential risks outlined below.

Kansui-related risks

Kansui is known to induce (and is used for the purpose of causing) a mild diarrhea as a means of eliminating excess water from the body in traditional Chinese medicine.^{8,9} Participants will be advised to read labels and check ingredients of foods to be sure to avoid products that may also induce diarrhea. Per traditional Chinese medical literature, common adverse events may include gastrointestinal irritability and headache, usually occurring within 30 minutes to 2 hours after ingestion.^{8,9} At very high doses (between 9 to 15 grams of kansui extract powder), kansui can cause dehydration with subsequent light-headedness, hypotension, and tachycardia. These high doses of kansui may also cause diarrhea with mucus and blood, pupillary dilation, convulsions, and unconsciousness. Participants for this study will be monitored closely for 8 hours after each dose of kansui and will be instructed to report any diarrhea with mucus or blood immediately to the study staff.

Virologic risk

Given that the purpose of studying kansui in this study is to evaluate whether it can reactivate HIV from latently infected cells, there is a risk that taking kansui for up to 3 days could lead to transient loss of viral suppression and subsequent development of resistance to the participant's current antiretroviral therapy. However, given the short duration of kansui administration and the predicted small increases in plasma viremia as a result of kansui, we believe that these risks will be low. Nonetheless, as per protocol with other currently studied latent reversing agents (LRAs), we will perform frequent plasma HIV RNA monitoring (screening, every dosing day, each 24-hour follow-up, and days 31 and 132) and even more frequent monitoring of the research-based reservoir measurements of cell-associated HIV DNA and RNA (see section 9.1 below). In addition, we will only enroll participants for whom alternative ART regimens are available in the event that their previously effective regimens are compromised. Finally kansui treatment will be discontinued if the participant has any two consecutive plasma HIV RNA levels levels >200 copies/mL, or any single plasma HIV RNA level >1000 copies/mL. These values would be above the levels predicted to be seen with HIV reactivation with most current latent reactivating agents and are safety stopping criteria currently used for other HIV latent reactivating agent trials, e.g., the AIDS Clinical Trials

Group (ACTG 5336) trial, evaluating the role of Sirolimus on immune activation and the latent reservoir in chronic HIV-infected, ART-suppressed individuals.

Reproductive risks

Given the unknown reproductive risks associated with kansui as tested scientifically, and its use in traditional Chinese medicine as an abortifacient,⁸ women of childbearing potential must have a negative serum pregnancy test in the medical workup for study entry and excluded from participation if pregnant. All participants must agree to use two forms of contraception throughout the study period and up to 90 days after the last dose of kansui (to account for the male sperm cycle). Women (or female partners of male study participants) must not breastfeed during the study period and up to 90 days after the last dose of kansui.

Confidentiality

As with any study collecting personal information in research records, this information could lead to loss of confidentiality. In particular, any study that collects genetic data poses the potential risk of loss of confidentiality that might be relevant to the study participant, relatives of the participant, and/or people with similar genetic background as the participant. Given that this particular study will not perform whole genome sequencing (DNA) data, but rather select RNA sequencing information, the risk of this occurring in this current study is minimal. However, in order to safeguard against this potential risk, genetic information pertaining to the study will not be placed in the participant's medical record. All samples will be labeled with de-identified codes, and the informed consent includes language to inform the participant of these risks, per NHGRI guidelines (<http://www.genome.gov/10000921#update>).

Potential discomforts

Potential discomforts of taking kansui include the bitter taste of the extract powder. Participants will be offered room temperature beverages or snack to alleviate discomfort due to the bitter taste. In addition, the requirement that participants avoid ice-cold beverages and ice-cold foods, may cause discomfort. The dietary restrictions will be for 48 hours prior to the first dose of kansui, during the days of kansui dosing, and up to 48 hours after the last dose of kansui.

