DURATION OF PARTICIPANT PARTICIPATION AND DURATION OF STUDY	
Cohort 1: Participants will be on study for up to 45 days.
 
Screening: up to 14 days
 
Treatment: 1 day (participants to be admitted to the hospital during the day; no overnight stay)
 
Follow-up: 31 days after treatment dose day
 
Cohort 2: Participants will be randomized to either of two treatment arms, kansui or placebo, using a crossover design with a 56-day washout period in between treatment arms. Participants will be on study for up to 146 days.
 
Screening (for each arm): up to 14 days prior to treatment arm.
 
Treatment (for each arm): 3 days (participants to be admitted to the hospital each day; no overnight stays)
 
Follow-up (for each arm): 31 days after the initial dose for that treatment arm.
 
The total duration of the study is expected to be 1 year.

CONCOMMITANT MEDICATIONS	
Allowed:
 
 1. In the absence of drug-drug interaction information regarding kansui, participants may use their usual medications, as long as they are medically necessary and can be monitored safely during the study period. 
Prohibited:
 
 1. As stated in the exclusionary criteria above, participants may not have exposure to any immunomodulatory drug (including maraviroc) in the 16 weeks prior to study or during study period. 2. Also as stated in the exclusionary criteria, participants may not have prior or current use of experimental agents used with the intent to perturb the HIV-1 viral reservoir. 3. Participants may not be allowed to take anti-motility agents during the study period in order to accurately assess adverse events related to diarrhea. 4. Participants will not initiate new medications that may also cause diarrhea, including proton pump inhibitors, antibiotics, antidepressants, colchicine, digitalis, etc., during the study period. 
In addition to the above medications, per traditional Chinese medicine practices, participants should also not ingest ice-cold food or beverages, spicy foods, or seafood in the two days prior to, during, and up to two days after kansui treatment.

EFFICACY EVALUATIONS	
 • CD4+ and CD8+ T cell activation (expression of CD69, CD38, and HLA-DR). • Latent HIV reservoir quantification (cell-associated HIV RNA and plasma HIV RNA levels).

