8.7 Measures of Treatment Compliance

Study participants will be monitored in the CCTS for directly observed therapy on the day(s) when *Euphorbia kansui* extract powder prepared as tea or placebo is administered. They will be receiving clinical and laboratory assessments on those days for up to 6 hours post-treatment.

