Parameter	Day -14 ^a	Day -7 ^a	Day 1	Day 1	Day 1	Day 2	Day 3	Day 3	Day 3	Day 4	Day 31	Day 32-87
	Tx #1 Screening	Baseline	Tx #1 0 hrs ^b	0.5 hrs ^b	2 hrs ^b	4 hrs ^b	0 hrs ^b	0.5 hrs ^b	2 hrs ^b	4 hrs ^b	24-hr post-dose follow-up	56-Day Washout Period
Informed consent	X											
Questionnaires	X	X	X				X	X			X	X
Demographics	X											
Medical history, medications, AE	X	X	X				X	X			X	X
Vital signs	X		X		X	X	X		X	X	X	X
Physical exam (either Complete / Targeted) ^c	X		X				X	X			X	X
Study kansui administration			X				X	X				
Complete blood count w/diff	X		X	X	X	X	X	X	X	X	X	X
Comprehensive Metabolic Panel	X		X				X	X			X	X
Quantiferon test (QFT)	X											
Pregnancy test (female participants)	X											X
TSH	X											
Hep B Ag	X											
HCV Ab	X											
CD4+/CD8+ T cell counts	X	X	X				X	X			X	X
HIV RNA: standard assay	X	X	X				X	X			X	X
Immune activation (CD69, CD38, HLA-DR)	X	X	X	X	X	X	X	X	X	X	X	X
HIV reservoir measures	X	X	X	X	X	X	X	X	X	X	X	X
PBMC and plasma cryopreservation for future studies (PK, transcriptome analyses)	X	X	X	X	X	X	X	X	X	X	X	X

No Study Procedures During Washout

^aDays -14, -7, 4, 31, 88, 102-105, and 132 represent the time from receiving the first dose of treatment on the Day 1 Visit.

^bHours 0, 0.5, 2, and 4 represent time from receiving treatment (*kansui* or placebo) on that dosing day.

^cThe complete physical exam must occur at screening visits (Day -14 and Day 88). In the event of an Early Withdrawal Visit a complete physical exam is to be performed. A targeted physical exam is to be completed for all other time points.

Study Events Table Cohort 2 (Treatment Phase 2)

Parameter	Day 88	Day 102	Day 102	Day 102	Day 102	Day 103	Day 104	Day 104	Day 104	Day 105	Day 132	Early Withdrawal Visit (if applicable)
	Tx #2 Screening	Tx #1 0 hrs ^a	0.5 hrs ^a	2 hrs ^a	4 hrs ^a	0 hrs ^a	0 hrs ^a	0.5 hrs ^a	2 hrs ^a	4 hrs ^a	24-hr post-dose follow-up	
Informed consent												
Questionnaires	X	X				X	X			X	X	X
Demographics												
Medical history, medications, AE	X	X				X	X			X	X	X
Vital signs	X	X		X	X	X	X		X	X	X	X
Physical exam (either Complete / Targeted) ^c	X	X				X	X			X	X	X
Study kansui administration		X				X	X					
Complete blood count w/diff	X	X	X	X	X	X	X	X	X	X	X	X
Comprehensive Metabolic Panel	X	X				X	X			X	X	X
Quantiferon test (QFT)	X											X
Pregnancy test (female participants)	X										X	X
TSH												
Hep B Ag												
HCV Ab												
CD4+/CD8+ T cell counts	X	X				X	X			X	X	X

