9.1.3 Dosing Day Procedures

1. For eligible participants, Day 1 will occur within 2 weeks of the screening visit. The 0.5, 2, and 4 hour visits noted below will occur within 30 minute windows. Participants will be free to leave the clinic in between the 0, 0.5, 2, and 4 hour visits.
2. 0 hours (prior to study drug administration that day)
 - a. History including concomitant medications and adverse event record
 - b. Follow-up questionnaires will be administered
 - c. Targeted physical examination & vital signs
 - d. Full blood examination (CBC, CMP)
 - e. HIV RNA: standard assay
 - f. Immune activation (CD69, CD38, HLA-DR expression on CD4+ and CD8+ T cells)
 - g. HIV reservoir: Given the potential for diurnal effect on the measures of HIV in resting cells, the first blood draw on this day will occur between 7:30 to 9:30 am.
 - i. Plasma HIV RNA (single copy assay)
 - ii. Cell associated HIV RNA (unspliced RNA) in CD4+ T-cells.
 - h. PBMC and plasma storage as below
3. 0.5 hours (after study drug administration that day)
 - a. CBC with differential
 - b. Immune activation
 - c. PBMC and plasma cryopreservation
4. 2 hours (after study drug administration that day)

- a. Vital signs
- b. CBC with differential
- c. Immune activation
- d. PBMC and plasma cryopreservation

5. 4 hours (after study drug administration that day)
 - a. Vital signs
 - b. CBC with differential
 - c. Immune activation
 - d. PBMC and plasma cryopreservation

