10.3 Monitoring

During the study, safety will be monitored by a Safety Monitoring Committee (SMC), which will be led by a qualified University of Utah faculty member in the Department of Medicine with expertise in HIV clinical research (see Section 13 below). The SMC will review all study procedures before the initiation of the study. They will have the full and final authority to stop the study for any safety concern at any point. The Principal Investigator at the University of Utah will be the primary medical monitor responsible for study adverse event monitoring and will report adverse events and unanticipated problems to the University of Utah IRB and the SMC. All participants will be followed for possible adverse events and unanticipated problems throughout the study period.

Participants will be monitored in an outpatient clinic during the first 4-6 hours post-dose on dosing days. At each visit, participants will be assessed for any new symptoms, and a study coordinator will obtain vital signs. The study will require 48-hour reporting of all laboratory values, signs/symptoms, and serious adverse events (SAEs). The study will have intensive Phase I safety monitoring, which will include regular and frequent team review (every week for the first 2 months of the study; then every two weeks thereafter) of all reported events. In addition, for any Grade 3 or 4 events, sites will be instructed to contact the study team by email.

- Grade 1 or 2 Toxicity: Participants who develop a Grade 1 or 2 AE or toxicity may continue study treatment. If a participant chooses to discontinue study treatment, the site should notify the kansui protocol core team as noted above, and encourage the participant to complete any remaining study visits.
- Grade 3 or 4 Toxicity: Participants experiencing Grade 3 or 4 AEs requiring permanent discontinuation of study treatment should be followed closely for resolution of the AE to Grade ≤ 2 and the protocol core team must be notified. Participants discontinuing study treatment should be encouraged to complete any remaining study visits.

[name] will be contacted directly to report medical concerns or questions regarding safety.

[contact]

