14.5 Sample Size

A total of 8 participants (2 in dosing cohort 1 and 6 in dosing cohort 2) will contribute to the analysis, with 8 or 25 timepoint measures, respectively. The within-individual variability will be reduced by repeated measurements post-dose. Based on existing data from our study population regarding the percent CD38+HLA-DR+ CD4+ T cells (standard deviation of 4.9%) in our study population and a paired, one sample, repeated measures analysis, we will have greater than 80% power to detect a 2.7% change in CD4+ T cell activation levels post-dose. Similarly, we will have greater than 80% power to detect a 17% change in cell-associated HIV-1 RNA and a 0.37% change in plasma HIV-1 RNA.

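### Section 2.1 states 8 hours of close monitoring after each kansui dose; the operational sections reach 6 hours at most, let participants leave between visits, and schedule no post-dose check on the second dosing day

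*Combined protocol and SAP*

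**What the plan says.** Section 2.1, where the benefits are judged to outweigh the risks, says "Participants for this study will be monitored closely for 8 hours after each dose of kansui". It also tells participants to report mucoid or bloody diarrhea to staff at once.

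The operational sections differ:

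- Section 10.3 (Monitoring): "Participants will be monitored in an outpatient clinic during the first 4-6 hours post-dose on dosing days".
- Section 8.7 (Treatment Compliance): clinical and laboratory assessments on dosing days "for up to 6 hours post-treatment".
- Section 9.1.3 (Dosing Day Procedures) and the events tables: time points at 0, 0.5, 2 and 4 hours, with vital signs after dosing at 2 and 4 hours. Nothing later is listed for that day.
- Section 9.1.3 on presence: "Participants will be free to leave the clinic in between the 0, 0.5, 2, and 4 hour visits".
- Section 8.4.3: staff observe side effects on the days of treatment, for kansui and for placebo.
- Synopsis: participants are admitted for the day on treatment days, with no number of hours given.

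For the second dosing day in Cohort 2, the Phase 2 events table gives Day 103 a single 0-hour column, and 9.1.3 defines 0 hours as before that day's dose. Section 9.4 excepts Days 2 and 103 from the usual post-dose pharmacokinetic draws and lists hour 0 only. Section 14.5 counts the measurements in Cohorts 1 and 2 "with 8 or 25 timepoint measures, respectively".

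**The concern.** This is a phase I trial with safety and tolerability as its primary endpoint, of a product whose safety profile 10.4 describes as unknown. The 8 hours in 2.1 are offered as a protection when the risk is weighed. Staff working from 10.3, 9.1.3 and the tables would deliver less than that.

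The permission to leave matters because of its timing. Section 2.1 places common reactions between 30 minutes and 2 hours after ingestion, and Section 2 places the bowel effect of a 1 g dose within two hours. A participant may be out of the clinic for most of that time.

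The second dosing day matters because tachycardia and light-headedness are among the solicited events (10.4), yet no vital signs are scheduled after that dose until the next morning.

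**Working it through.** **Duration.** The statements side by side:

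| Source | Hours after dose |
|---|---|
| 2.1 | 8, close monitoring |
| 10.3 | 4 to 6, in clinic |
| 8.7 | up to 6, assessments |
| 9.1.3 and tables | last itemised procedure at 4 |

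The longest operational period is 6 hours. Shortfall: 8 − 6 = 2 hours, and 2/8 = 25%. This is the part that no operational section covers. The Cohort 1 example in 9.4 names a 6-hour pharmacokinetic draw that is in neither that section's opening list nor the tables. It is probably a slip for 4, and even if genuine it does not reach 8.

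Section 2.1 does not say that the 8 hours are on site, so off-site contact could fill the gap. None is scheduled: the next planned contact is the following day's visit in both cohorts.

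**Presence.** The 0.5- and 2-hour visits sit at the two ends of the onset window in 2.1. The nominal gap between them is 2 − 0.5 = 1.5 hours, during which 9.1.3 allows absence. With the 30-minute visit windows the actual gap can be shorter or longer. Free departure does not fit close monitoring (2.1), monitoring in a clinic (10.3) or staff observation of side effects (8.4.3).

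**Second dosing day.** Day 103 can be read from the Phase 2 table: one column, 0 hours, one vital-signs entry. The Phase 1 table does not show its Day 2 column cleanly in the copy reviewed, so Day 2 rests on two other sources.

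1. Section 9.4 lists Days 2 and 103 together, at hour 0 only.
2. The count in 14.5. As a check on the method, Cohort 1 has Day −14, Day −7, four on Day 1, Day 2 and Day 31: 1 + 1 + 4 + 1 + 1 = 8, as stated. For Cohort 2 with one time point on Days 2 and 103:
   - Phase 1: Day −14, Day −7, Day 1 (4), Day 2 (1), Day 3 (4), Day 4, Day 31 = 13.
   - Phase 2: Day 88, Day 102 (4), Day 103 (1), Day 104 (4), Day 105, Day 132 = 12.
   - Total: 13 + 12 = 25, as stated.
   - With 0.5, 2 and 4 hours added on both days: 25 + 2 × 3 = 31, which does not match.

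The count fits a single visit on Day 2; it does not replace a reading of the table. Together with 9.4 it makes a pre-dose visit only on both days the likely intention for blood sampling. By contrast, 9.1.3, 8.7, 8.4.3 and 10.3 make no exception for the second dosing day when they describe post-dose procedures and observation.

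**The case against.** The strongest reply is that the operational sections agree well enough on duration: 4 to 6 hours in clinic, assessments up to 6, last itemised procedures at 4. On that view the only error is one number in a narrative section, and 10.3 gives the working rule. Much of this stands. It settles which number is likely to be corrected, but not the permission to leave or the second dosing day.

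It is also fair that the 0.5- and 2-hour visits bracket the expected onset, that 10.3 has new symptoms assessed and vital signs taken at each visit, and that the severe effects in 2.1 are described at 9 to 15 g, not 1 g. The immediate-reporting instruction, the 5-day hold after the first participant at each dose level and the stopping rules also remain. A required stay to 2 hours and an added check go somewhat beyond correcting wording.

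Four stronger readings are tempting, and the documents do not support them:

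- **Half of the 8 hours is missing (8 − 4 = 4).** Section 9.1.3 lists procedures and does not say that observation ends at 4 hours; 10.3 and 8.7 extend to 6. A site working to the lower end of 10.3 could stop at 4, but the part covered by no section is 2 hours.
- **The second-day kansui doses, 6 of 20 (2 × 1 + 6 × 3 = 20; 30%), go unobserved.** That requires the tables to override 10.3 and 8.4.3, which apply observation to all dosing days. Section 14.5 counts measurements, not safety contacts.
- **Nothing indicates which text governs.** Sections 9 and 9.1 describe the tables as the full schedule. That is a pointer, though not a rule of precedence.
- **The primary endpoint is compromised.** On dosing days the adverse-event record is itemised only at 0 hours. However, the 0-hour record on later dosing days follows the previous dose, events are also recorded at the 24-hour and Day 31 or 132 visits, and 10.1 requires the investigator to probe for events at every visit.

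**Conclusion.** The inconsistency is real and lies between current sections of the protocol. Section 2.1 states a protection that the procedures do not deliver: at least 2 of 8 hours (25%) have no operational counterpart, and no contact is scheduled before the next day. The permission to leave conflicts with 2.1, 10.3 and 8.4.3 during the expected onset window. On the second dosing day no post-dose vital signs or adverse-event check is scheduled, although the text applies observation to every dosing day. For Day 2 this rests on 9.4 and the count of 25; for Day 103 it is read directly from the table.

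The change should be made because the trial's purpose is safety and the change is cheap. The likely effect on the primary endpoint is small. Sample size, power, error rates and stopping rules are unaffected.

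**What to change.** 1. State one post-dose observation period in 2.1, 8.7, 9.1.3 and 10.3. If 4 to 6 hours is kept, correct the 8 in 2.1. If 8 hours is meant to include off-site contact, say how and when.
2. Replace the free-to-leave sentence in 9.1.3 with a requirement to stay at least until the 2-hour assessment.
3. Add a post-dose vital-sign and adverse-event check on Days 2 and 103 to the events tables, with no extra blood draw. Doing this in both phases keeps the blind, and the 25 time points in 14.5 stand.

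The cost is wording, table entries and some extra clinic time on dosing days. Keeping 4 to 6 hours adds nothing beyond 10.3; choosing 8 hours on site adds 2 to 4 hours per dosing day (8 − 6 to 8 − 4). The stay to 2 hours should be a modest burden: 8.4.3 already limits participants to crackers and juice until after the 2-hour draw.
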